7.0 Protocol Treatment

7.1 Treatment Schedule – Use actual weight with dose adjustments if weight changes more than 10% from baseline.

Cycle = 28 days

Agent	Route	Day
Nanoliposomal Irinotecan (nal-IRI)	IV	Days 1 and 15
Leucovorin (LV)*	IV	Days 1 and 15, prior to 5-FU
Fluorouracil (5-FU)	IV	Days 1 and 15
Rucaparib	PO	Twice each day on Days 4-13 and Days 18-27 of a 28 day cycle.

*If there is a shortage of leucovorin (LV) in the U.S., and you are unable to obtain access, LV may be held until supply is available. LV will not be administered in the phase Ib/II portion of the study

7.11 Planned Phase I Dose Escalation Levels:

Dose Level	Agent	Dose	Route	Day
DL-2	Nanoliposomal irinotecan (nal-IRI)	43 mg/m2	Intravenous over 90 minutes	Days 1 and 15
	Leucovorin (LV)	400 mg/m2	Intravenous	Days 1 and 15, prior to 5-FU
	Fluorouracil (5-FU)	2000 mg/m2	Intravenous over 46 hours	Days 1 and 15
DL-1	Rucaparib	200 mg	Oral	Twice daily on Days 4-13 and 18-27
	nal-IRI	50 mg/m2	Intravenous over 90 minutes	Days 1 and 15
	LV	400 mg/m2	Intravenous	Days 1 and 15, prior to 5-FU
	5-FU	2400 mg/m2	Intravenous over 46 hours	Days 1 and 15
DL1*	Rucaparib	200 mg	Oral	Twice daily on Days 4-13 and days 18-27
	nal-IRI	50 mg/m2	Intravenous over 90 minutes	Days 1 and 15
	LV	400 mg/m2	Intravenous	Days 1 and 15, prior to 5-FU
	5-FU	2400 mg/m2	Intravenous over 46 hours	Days 1 and 15
DL2-A	Rucaparib	400 mg	Oral	Twice daily on Days 4-13 and days 18-27
	Nanoliposomal irinotecan (nal-IRI)	50 mg/m2	Intravenous over 90 minutes	Days 1 and 15
	Fluorouracil (5-FU)	2400 mg/m2	Intravenous over 46 hours	Days 1 and 15
DL 2-B	Rucaparib	600 mg	Oral	Twice daily on Days 4-13 and days 18-27
	nal-IRI	70 mg/m2	Intravenous over 90 minutes	Days 1 and 15
	LV	400 mg/m2	Intravenous	Days 1 and 15, prior to 5-FU
	5-FU	2400 mg/m2	Intravenous over 46 hours	Days 1 and 15
DL 3	Rucaparib	400 mg	Oral	Twice daily on Days 4-13 and days 18-27
	nal-IRI	70 mg/m2	Intravenous over 90 minutes	Days 1 and 15
	Leucovorin	400 mg/m2	Intravenous	Days 1 and 15, prior to 5-FU
	5-FU	2400 mg/m2	Intravenous over 46 hours	Days 1 and 15
	Rucaparib	600 mg	Oral	Twice each day on

				Days 4-13 and days 18-27
--	--	--	--	--------------------------

* Starting dose level

Only patients with pancreatic, colorectal, gastroesophageal and biliary tract cancers will be included

7.12 Phase Ib Dose Expansion (Phase Ib Study at recommended dose level determined by the Phase I portion):

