7.42 Definitions of DLT

Toxicity will be assessed using the NCI CTCAE, version 4.03 unless otherwise specified. A DLT is defined as an AE or abnormal laboratory value (assessed as possibly, probably or definitely related to the study medication) which occurs \leq 28 days following the first dose of MFR (or 1 cycles of therapy, each cycle = 28 days), and meets any of the criteria listed in Table 7.421.

If a patient experiences toxicity that fulfills the criteria for a DLT during the DLT observation window (cycle 1 day 1 through cycle 1 day 28, treatment with the study drug will be interrupted and the toxicity will be followed up. Patients will be allowed to remain on study if the DLT is resolved within 4 weeks at the discretion of the investigator. Patients will continue on study at the next lowest dose level. If treatment is reduced during the DLT observation window or is held for >28 days for any reason, this will be considered a DLT.

7.421 Dose Limiting Toxicities (DLT)

TOXICITY	DLT CRITERIA
Hematology	CTCAE grade 4 neutropenia with fever of any duration, or grade 4 neutropenia lasting more than 5 consecutive days
	CTCAE grade 4 thrombocytopenia lasting more than 5 days, or grade 3 with bleeding
	CTCAE Grade 3 or 4 neutropenia with fever (temperature $\geq 38.5^{\circ}\text{C}$)
Skin and subcutaneous tissue disorders	Rash, hand-foot skin reaction or photosensitivity CTCAE Grade 3 lasting more than 7 consecutive days despite skin toxicity treatment (as per local practice)
Gastro-intestinal	CTCAE grade ≥ 3 nausea or vomiting lasting more than or equal to 48 hrs despite optimal anti-emetic therapy
	CTCAE grade ≥ 3 diarrhea lasting more than or equal to 48 hrs despite optimal anti-diarrhea treatment
Hepatobiliary	CTCAE grade ≥ 3 total bilirubin (excluding any elevations caused by mechanical obstruction of the biliary tree by tumor or stent blockage)
	CTCAE grade ≥ 4 ALT (isolated increases in AST without concomitant increases in ALT will not be considered dose-limiting, because of the non-specific nature of AST)
	Serum alkaline phosphatase CTCAE Grade 4 lasting more than 7 consecutive days
ECG QTc Interval	QTc interval ≥ 501 ms on at least two separate consecutive ECGs taken 5 min apart
Renal	Serum creatinine $> 6x$ ULN
Non-hematologic events	Any non-hematological CTCAE grade ≥ 3 , except for the exclusions noted below
Other	Any related toxicity that delays treatment by > 28 days
Exceptions to DLT criteria	CTCAE grade 3 fatigue lasting fewer than 5 days

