13.0 Treatment/Follow-up Decision at Evaluation of Patient

13.1 Patients who are CR, PR, or SD will continue treatment per protocol. Patients who are CR, PR, or SD at time of their reassessment and **have not** experienced intolerable toxicity will be allowed to continue protocol treatment at the same dose level until PD or maximum of 3 years whichever is earlier.

Those patients who are CR, PR, or SD but **have** experienced unacceptable toxicity may be eligible for retreatment at a lower dose until PD or maximum of 3 years whichever is earlier, at discretion of treating physician (see Section 8.0).

13.2 Patients who develop PD while receiving therapy will go to the event-monitoring phase. Treatment decision during event-monitoring phase is at the discretion of the treating physician.

13.3 Patients who go off protocol treatment for reasons other than PD will go to the event-monitoring phase per Section 18.0. Treatment decision during event-monitoring phase is at the discretion of the treating physician.

13.4 If a patient enrolled to Phase I dose escalation part of the study fails to complete the initial course of therapy (defined as drug administration \leq 75% of expected cycle 1 total dose) for reasons other than dose-limiting toxicity defined adverse events, the patient will be regarded as uninformative in regard to the primary study goal and an additional patient will be enrolled at the current dose level

13.5 A patient is deemed *ineligible* if after registration, it is determined that at the time of registration, the patient did not satisfy each and every eligibility criteria for study entry. The patient may continue treatment off-protocol at the discretion of the physician as long as there are no safety concerns, and the patient was properly registered. The patient will go directly to the event-monitoring phase of the study (or off study, if applicable).

- If the patient received treatment, all data up until the point of confirmation of ineligibility must be submitted. Event monitoring will be required per Section 18.0 of the protocol.
- If the patient never received treatment, on-study material must be submitted. Event monitoring will be required per Section 18.0 of the protocol.

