16.13 Accrual Rate and Study Duration

The anticipated accrual rate for Phase I is 1 patient per month. At this rate, it will likely take about 4 months to enroll, treat, and evaluate each set of 3 patients in the phase I portion of this study. The phase I portion is expected to take between 12 and 24 months.

The anticipated accrual rate for Phase Ib is 3-4 pancreatic cancer patients per month. The phase Ib portion is expected to take up to 20 months.

The anticipated screening rate for Phase II portion is approximately 8-10 patients per month. The anticipated accrual rate for Phase II is approximately 1-2 patients per month for patients with untreated pancreatic cancer with HRD encompassing BRCA1, BRCA2 and PALB2 patients. Therefore, the accrual period is expected to be between 12 and 24 months, depending upon whether the trial will continue accruing patients beyond the interim analysis.

The total study duration is expected to be approximately 24 to 48 months until the last patient accrued in the Phase II portion has been observed for at least 4 months.

16.2 Phase I portion:

The phase I portion of this trial is a single arm phase I study utilizing cohort-of-3 design to determine the recommended dose level of the combination of nal-IRI and 5FU with rucaparib (MFR) in patients with metastatic disease from pancreatic cancer (up to 2 lines of prior therapy), colorectal cancer (up to 3 lines of prior therapy), gastroesophageal cancer (up to 1 line of prior therapy) and biliary tract cancer (BTC; up to 1 line of prior therapy allowed).

Decisions regarding the reopening of the cohort to new patients, the expansion of any other cohort, and the need to dose reduce patients already receiving treatment at the dose level in question will be made by the Study Chair(s).

All patients meeting the eligibility criteria who have signed a consent form and have received one dose of MFR will be included in the analysis. Patients removed from the study during cycle 1 for reasons other than toxicity maybe replaced.

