16.22 MTD Determination

- 16.221 The first cohort of three patients will be treated at the starting dose level (DL1).
- 16.222 Three patients will be treated at a given dose level and observed for at least 4 weeks (Cycle 1) from start of treatment to assess toxicity.
- 16.223 If DLT is not seen in any of the 3 patients, 3 new patients will be accrued and treated at the next higher dose level. If DLT is seen in 2 or 3 of 3 patients treated at a given dose level, then the next 3 patients will be treated at the next lower dose level, if only 3 patients were enrolled and treated at this lower dose level.
- 16.224 If DLT is seen in 1 of 3 patients treated at a given dose level, up to 3 additional patients will be enrolled and treated at the same dose level. If DLT is seen in at least one of these additional three patients (≥ 2 of 6), the MTD will have been exceeded, and further accrual will cease to this cohort (see 16.223 for further details). If dose-limiting toxicity (DLT) is not seen in any of the three additional patients, 3 new patients will be accrued and treated at the next higher dose level.
- 16.225 After enrolling 6 patients on a specific dose level, if DLT is observed in at least 2 of 6 patients, then the MTD will have been exceeded and defined as the previous dose unless only 3 patients were treated at the lower dose level. In that case, 3 additional patients will be treated at this lower dose level such that a total of 6 patients are treated at the MTD to more fully assess the toxicities associated with the MTD.
- 16.226 Dose de-escalation: If dose-limiting toxicity meets the stopping boundaries set by the above dose escalation algorithm at dose level 1 (for example, more than 1 out of 3 patients or more than 1 out of 6 patients), the next cohort of three patients will be entered at a dose level of -1. Further dose re-escalation will depend on the toxicity profile observed at dose level -1, and re-evaluation of the regimen by the study team may be done.
- 16.227 If a patient fails to complete the initial course of therapy (See Section 13.4) and did not have a DLT while on study, the patient will be regarded as uninformative in regard to the primary study goal and an additional patient will be treated at the current dose level; however, all toxicity information will be utilized in the analysis.

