16.43 Phase II Analysis Plan

16.431 Primary Endpoint Analysis - Estimation: The proportion of best response ≤ 32 weeks will be estimated by the number of evaluable patients who reach CR/PR, per RECIST 1.1, ≤ 32 weeks since registration divided by the total number of evaluable patients. Confidence intervals for the proportion will be calculated according to the approach of Duffy and Santner (1987).

16.432 Secondary Endpoint Analyses

16.432a Overall survival: Survival time is defined as the time from registration to death due to any cause. Patients who fail to return for evaluation after beginning therapy will be censored for survival on the last day of therapy or date last known to be alive, whichever is later. The distribution of survival time will be estimated using the method of Kaplan-Meier (1958).

16.432b Progression-free survival: Progression-free survival is defined as the time from registration to the earliest date documentation of disease progression or death due to any cause. Patients who fail to return for evaluation after beginning therapy will be censored for progression on the last day of therapy or date last known to be alive, whichever is later. The distribution of progression-free

survival will be estimated using the method of Kaplan-Meier (1958).

16.432c Toxicity: As per NCI CTCAE version 4.03, the term toxicity is defined as adverse events that are classified as either “possibly,” “probably,” or “definitely related” to study treatment. The maximum grade for each type of toxicity will be recorded for each patient, and frequency tables will be reviewed to determine toxicity patterns within patient groups. In addition, we will review all adverse event data that is graded as 3, 4, or 5 and classified as either “unrelated” or “unlikely to be related” to study treatment in the event of an actual relationship developing. Adverse events and toxicities will be evaluated using all patients who have received any study treatment as well as summarizing those who have been included in the efficacy analyses. The overall adverse event rates for grade 3 or higher adverse events will be compared using Chi-Square or Fisher’s Exact tests between the two treatment groups.

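### The Phase I analysis set in 16.2 is conditioned on eligibility, so some treated patients later found ineligible fall outside the stated set for toxicity and DLT summaries

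*Combined protocol and SAP*

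**What the plan says.** Section 16.2 (Phase I portion) states: "All patients meeting the eligibility criteria who have signed a consent form and have received one dose of MFR will be included in the analysis". No other Phase I analysis set is defined. Section 16.231 then tabulates adverse events for the patient population without naming a separate safety set.

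Section 13.5 makes a patient ineligible if it emerges after registration that "the patient did not satisfy each and every eligibility criteria for study entry". For treated patients it requires data to be submitted up to the point when ineligibility is confirmed. It does not say whether those data enter the Phase I analysis.

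Section 16.227 covers patients who do not complete the initial course and had no DLT. They are replaced for the dose decision; "however, all toxicity information will be utilized in the analysis".

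Phase II uses a different rule. Section 16.432c says: "Adverse events and toxicities will be evaluated using all patients who have received any study treatment".

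MFR is the "combination of nal-IRI and 5FU with rucaparib (MFR"). In the 7.1 schedule, nal-IRI and 5-FU are given on day 1, and rucaparib is taken "Twice each day on Days 4-13 and Days 18-27 of a 28 day cycle".

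**The concern.** The Phase I endpoint is the incidence of DLTs (16.11). Whether a drug harmed a patient does not depend on a later finding that an entry criterion was missed. A safety set that requires eligibility can therefore only lose toxicity information, and at small dose levels each patient counts. It also leaves one protocol with two safety populations and no reason given, so Phase I and Phase II toxicity tables would not be built on the same basis.

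A second, smaller issue is that one dose of MFR is not defined for a combination whose third drug starts three days after the first two.

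**Working it through.** **1. The plan's own figure.** Section 16.21 takes six patients at the MTD and a toxicity of 25% incidence. The chance of seeing it at least once is 1 − (1 − 0.25)^6 = 1 − 0.178 = 0.822. This reproduces the stated 82%.

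**2. Which treated Phase I patients the text covers.**
- *Eligible, completed cycle 1:* inside the 16.2 set.
- *Stopped early, no DLT:* 16.227 keeps the toxicity data. This plausibly also covers an ineligible patient removed early. Section 13.4 defines non-completion as receiving 75% or less of the expected cycle 1 dose.
- *Eligible, stopped early because of a DLT:* 13.4 makes a patient uninformative only when the reason is something other than a DLT, so the DLT counts.
- *Later found ineligible, and had a DLT or completed cycle 1:* fails the eligibility condition in 16.2 and does not meet the terms of 16.227. No Phase I text brings this patient back into the summaries.

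The last group is the gap.

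**3. Day 1 to day 3 stoppers.** Section 7.42 counts DLTs up to "28 days following the first dose of MFR" and describes toxicity "during the DLT observation window (cycle 1 day 1 through cycle 1 day 28". Read together, the first dose of MFR is the day 1 dose, before rucaparib. With 13.4 and 16.227, early stoppers are kept whether or not they had a DLT.

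**4. Other provisions that use treated patients.** The 16.521 Phase I/Ib stopping rule counts treated patients with no eligibility condition. Sections 16.222 to 16.225 and 16.228 count patients treated at a dose level, also without one.

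**5. Illustration of size.** Assume one of six treated patients is left out as ineligible and not replaced. The chance in step 1 becomes 1 − 0.75^5 = 1 − 0.237 = 0.763, or 76%. The loss is 82.2 − 76.3 = 5.9 percentage points. This shows the effect of one exclusion; it does not estimate how often one occurs.

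**The case against.** The strongest reply is that little is lost in practice. Related adverse events of every grade are collected in Phase I/Ib (10.531), the stopping rule and the escalation rules use treated patients, and 13.5 requires data from treated ineligible patients. Registration checks eligibility (6.113) and no waivers are allowed (3.0), so such patients may be few. The population wording in 16.231 can also be read as the tumour population rather than the 16.2 set. All of this stands as a limit on importance. It does not close the gap: 16.2 is the only sentence defining who is analysed in Phase I, and it requires eligibility.

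A reader might infer three stronger points, which the documents do not support.
- *Patients who stop before rucaparib on day 4 are dropped.* Sections 7.42, 13.4 and 16.227 indicate that they are kept. The wording is ambiguous, but it is not an exclusion.
- *The MTD could be reversed,* for example 2 of 6 (33%) becoming 1 of 5 (20%). The escalation rules count treated patients, 16.225 calls for six at the MTD, and 7.12 already records DL2-A as the recommended dose.
- *The likely loss can be quantified from the Phase II allowance of 3 in 24 (12.5%).* That allowance (16.12) also covers cancellations, who by 13.7 were never treated, and major violations. It is not a rate of treated patients later found ineligible.

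Nor does Phase Ib restrict its toxicity tables. The evaluable set in 16.32 is for disease control. Phase Ib simply names no safety set, although tolerability is part of its primary aim (2.21).

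**Conclusion.** The point holds in a narrow form. As written, 16.2 leaves a treated patient later found ineligible, who had a DLT or completed cycle 1, outside the stated set for Phase I toxicity and DLT summaries, unlike Phase II. The size is unknown because no ineligibility rate is given. The fall from 82% to 76% rests on the assumption of one unreplaced exclusion among six patients. The consequence is for Phase I safety reporting; nothing here shows that a dose decision was or would be changed. The phrase about one dose of MFR needs a definition, but the surrounding sections point to the inclusive reading. The correction is worth making because it is nearly free.

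**What to change.** - **Section 16.2:** state that every patient who received any dose of any study drug is included in all Phase I adverse event, toxicity and DLT summaries, regardless of eligibility, in line with 16.432c. This also settles what one dose of MFR means.
- **DLT table:** show the count at each dose level with and without patients later found ineligible.
- **Section 16.233:** keep a set of eligible, consented patients who received any study drug, for the Phase I response summary only.
- **Section 16.3:** state the same all-treated set for Phase Ib toxicity, and leave the 16.32 evaluable set for disease control unchanged.

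The cost is a few sentences and one extra line in the DLT table. No new data are needed: 13.5 already requires data from treated patients up to confirmation of ineligibility. No treatment or escalation rule changes.

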16.22 MTD Determination

- 16.221 The first cohort of three patients will be treated at the starting dose level (DL1).
- 16.222 Three patients will be treated at a given dose level and observed for at least 4 weeks (Cycle 1) from start of treatment to assess toxicity.
- 16.223 If DLT is not seen in any of the 3 patients, 3 new patients will be accrued and treated at the next higher dose level. If DLT is seen in 2 or 3 of 3 patients treated at a given dose level, then the next 3 patients will be treated at the next lower dose level, if only 3 patients were enrolled and treated at this lower dose level.
- 16.224 If DLT is seen in 1 of 3 patients treated at a given dose level, up to 3 additional patients will be enrolled and treated at the same dose level. If DLT is seen in at least one of these additional three patients (≥ 2 of 6), the MTD will have been exceeded, and further accrual will cease to this cohort (see 16.223 for further details). If dose-limiting toxicity (DLT) is not seen in any of the three additional patients, 3 new patients will be accrued and treated at the next higher dose level.
- 16.225 After enrolling 6 patients on a specific dose level, if DLT is observed in at least 2 of 6 patients, then the MTD will have been exceeded and defined as the previous dose unless only 3 patients were treated at the lower dose level. In that case, 3 additional patients will be treated at this lower dose level such that a total of 6 patients are treated at the MTD to more fully assess the toxicities associated with the MTD.
- 16.226 Dose de-escalation: If dose-limiting toxicity meets the stopping boundaries set by the above dose escalation algorithm at dose level 1 (for example, more than 1 out of 3 patients or more than 1 out of 6 patients), the next cohort of three patients will be entered at a dose level of -1. Further dose re-escalation will depend on the toxicity profile observed at dose level -1, and re-evaluation of the regimen by the study team may be done.
- 16.227 If a patient fails to complete the initial course of therapy (See Section 13.4) and did not have a DLT while on study, the patient will be regarded as uninformative in regard to the primary study goal and an additional patient will be treated at the current dose level; however, all toxicity information will be utilized in the analysis.
- 16.228 DL2-A (formerly known as DL1-A) was added as an intermediate dose level between DL 1 and DL2-B (formerly known as DL2) (Amendment 3). Following the approval of Amendment 3, enrollment will re-open to DL2-A. If DLTs are seen in less than 2 out of 6 patients treated at DL2-A then DL2-A will be considered the MTD. If DLTs are observed in at

least 2 patients treated at DL2-A then enrollment will resume at the next lowest DL until MTD is met.

- 16.23 Analysis plans: All the relevant results pertaining to toxicity, MTD, laboratory correlates will be examined in an exploratory and hypothesis-generating fashion.
- 16.231 Adverse events profile: The number and severity of all adverse events (overall, by dose-level, and by tumor group) will be tabulated and summarized in this patient population. The grade 3+ adverse events will also be described and summarized in a similar fashion. This will provide an indication of the level of tolerance for this treatment combination in this patient group
- 16.232 Toxicity Profile: The term toxicity is defined as adverse events that are classified as either possibly, probably, or definitely related to study treatment. Non-hematologic toxicities will be evaluated via the ordinal CTC standard toxicity grading. Hematologic toxicity measures of thrombocytopenia, neutropenia, and leukopenia will be assessed using continuous variables as the outcome measures (primarily nadir) as well as categorization via CTC standard toxicity grading. Overall toxicity incidence as well as toxicity profiles by dose level, patient and tumor site will be explored and summarized.
- 16.233 Response: Objective responses, as defined per RECIST 1.1, will be summarized by simple descriptive summary statistics delineating complete and partial responses as well as stable and progressive disease.

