10.52 Baseline and Adverse Events Evaluations

“Investigators should complete all routine and standard of care assessments to evaluate for toxicity and symptoms of drug-induced adverse events. This may include, but is not limited to, verbal reports from the patient and/or caregiver, physical examination and laboratory findings. Adverse events should be reported throughout the course of the study, until the study termination visit, and followed through to resolution”.

10.521 Adverse events to be graded at each evaluation and pretreatment symptoms/conditions to be evaluated at baseline per the CTCAE v4.0 grading:

System Organ Class	Adverse Event Symptom(s)	Baseline	Each Evaluation
Blood and lymphatic system disorders	Febrile neutropenia		X
Gastrointestinal	# stools per day	X	
	Diarrhea		X
	Nausea	X	X
	Vomiting	X	X
General disorders and administration site conditions	Edema limb	X	X
	Periorbital edema	X	X
	Fatigue	X	X
Investigations	Aspartate aminotransferase (AST) increase	X	X
	Alanine aminotransferase (ALT) increase	X	X
	Alkaline phosphatase, serum (ALK) increase	X	X
	Blood Bilirubin increase	X	X
	Neutrophil count decrease	X	X
	Platelet count decrease	X	X
Metabolism and nutrition disorders	Hypokalemia	X	X
Renal and urinary disorders	Serum creatinine increase	X	X

10.53 Submit via appropriate Academic and Community Cancer Research United (ACCRU) Case Report Forms (i.e., paper or electronic, as applicable) the following AEs experienced by a patient and not specified in Section 10.5:

10.531 Phase I/Ib:

All AEs deemed *possibly, probably, or definitely* related to the study treatment or procedure, regardless of Grade

10.532 Phase II:

Grade 1-2 AEs deemed *possibly, probably, or definitely* related to the study treatment or procedure.

Grade 3 and 4 AEs regardless of attribution to the study treatment or procedure.

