15.17 Known potential adverse events:**Common known potential toxicities (> 10%):**

Asthenia, fatigue, anemia, increased ALT/AST, thrombocytopenia, nausea, vomiting, diarrhea, increased serum creatinine, decreased appetite, constipation, abdominal pain, dyspepsia, dysgeusia, dizziness, dyspnea, pyrexia, insomnia, photosensitivity reaction

Less common known potential toxicities (1% - 10%):

Leukopenia, lymphopenia, decreased WBC, increased serum cholesterol, hypercholesterolemia, increased transaminases, decreased lymphocyte count, decreased neutrophil count, hypophosphatemia, febrile neutropenia, upper respiratory tract infection, Myelodysplastic Syndrome, Acute Myeloid Leukemia

Rare known potential toxicities, <1% (Limited to important or life-threatening):

Pneumonitis

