16.3 Phase Ib portion

The phase Ib portion of this trial consists of an expansion cohort of patients with metastatic disease from pancreatic adenocarcinoma who have received no more than 1 line of prior therapy in the metastatic setting. Patients will be separated into two cohorts based on their HRD status (section 5).

- 16.31 Analysis plans: All the relevant results pertaining to toxicity, MTD, laboratory correlates will be examined in an exploratory and hypothesis-generating fashion.
- 16.32 Disease control (DC) is defined as achieving CR, PR, or maintaining SD (per RECIST v1.1) as the tumor assessment result for at least 24 weeks. Disease Control Rate will be estimated by the number of evaluable patients achieving disease control divided by the total number of evaluable patients. Evaluable patients for the primary endpoint are defined as who have signed the consent form, are eligible, received any protocol treatment. Point estimates will be generated for disease control rates within each cohort along with 95% binomial confidence intervals. (Clopper, C.J and E.S. Pearson, *The Use of Confidence or Fiducial Limits Illustrated in the Case of Binomial*. *Biometrika*, 1934.**26**(4).: p. 404-413).

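### In Phase I/Ib, non-serious anemia judged unlikely or unrelated has no stated route to the AE forms, so the tabulated anemia rate depends on attribution

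*Combined protocol and SAP*

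**What the plan says.** **Collection.** Section 10.521 is headed "Adverse events to be graded at each evaluation and pretreatment symptoms/conditions to be evaluated at baseline per the CTCAE v4.0 grading". It sets no attribution condition. Neutrophil and platelet decrease have rows at baseline and at each evaluation; anemia has neither. For events outside the solicited list, 10.531 tells Phase I/Ib sites to submit those possibly, probably or definitely "related to the study treatment or procedure, regardless of Grade". Phase II is wider: 10.532 also takes "Grade 3 and 4 AEs regardless of attribution to the study treatment or procedure".

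**Known toxicity.** Rucaparib's list of toxicities above 10% (15.17) begins "Asthenia, fatigue, anemia, increased ALT/AST, thrombocytopenia, nausea, vomiting, diarrhea, increased serum creatinine".

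**Analysis, Phase I.** Section 16.231 states: "The number and severity of all adverse events (overall, by dose-level, and by tumor group) will be tabulated and summarized". Grade 3+ events are to be described the same way. Section 16.232 defines toxicity as adverse events at least possibly related, then says "Hematologic toxicity measures of thrombocytopenia, neutropenia, and leukopenia will be assessed using continuous variables as the outcome measures (primarily nadir"), with CTC grading as well. Hemoglobin is not in that list.

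**Analysis, Phase Ib.** Section 16.31 offers one general sentence: "All the relevant results pertaining to toxicity, MTD, laboratory correlates will be examined in an exploratory and hypothesis-generating fashion".

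**Analysis, Phase II.** Section 16.432c adds a check on attribution: "we will review all adverse event data that is graded as 3, 4, or 5 and classified as either" unrelated or unlikely to be related.

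**The concern.** A table presented as covering all adverse events should count each event by the same rule. Here, neutrophil and platelet decreases enter whatever the investigator thinks of the cause, while non-serious anemia enters only if the investigator accepts at least a possible link to treatment. The two rates would sit side by side and mean different things.

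Attribution is plausibly an issue for anemia. Section 3.17 admits patients with hemoglobin just above 9.0 g/dL, so some low values will predate treatment and may be put down to the disease. With no baseline row in 10.521, the solicited data cannot show whether hemoglobin worsened.

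At stake is the description of the combination's hematologic tolerability. Further tolerability is part of the Phase Ib primary aim (2.21), although the only endpoint defined for that objective is disease control rate (16.11) and the phase is exploratory (16.12).

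**Working it through.** **1. Solicited list against the known-toxicity list.** Section 10.521 grades 15 terms at each evaluation, of which 8 are laboratory values: AST, ALT, alkaline phosphatase, bilirubin, neutrophils, platelets, potassium and creatinine. The laboratory-measured items on rucaparib's above-10% list compare as follows.

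| Item in 15.17 | Row in 10.521 |
|---|---|
| ALT | yes |
| AST | yes |
| Thrombocytopenia | yes |
| Serum creatinine | yes |
| Anemia | no |

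Four of five are solicited; anemia is the one left out.

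**2. Routes by which Phase I/Ib anemia reaches the AE forms.**

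| Anemia event | Route |
|---|---|
| At least possibly related, any grade | 10.531 |
| Serious, any attribution | 10.311 (expedited), then routine forms under 10.1 item g |
| Death within 30 days of last treatment, any attribution | 10.541 |
| Non-serious, unlikely or unrelated | none stated |

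**3. Consequence for each analysis section.**
- 16.231 (all events and grade 3+ events): the last row of the table above is missing, so the anemia rate is filtered by attribution.
- 16.232 (toxicity, meaning related events): nothing is missing from the AE data, because 10.531 collects every related event. The omission here is only that hemoglobin is not named for nadir and grade.
- 16.31 (Phase Ib): no table is specified, so any anemia rate taken from the AE forms carries the same filter.

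**4. The plan's own detection figure.** Section 16.21 says a toxicity with 25% incidence will be seen among 6 patients with probability at least 82%. Check: 1 − (1 − 0.25)^6 = 0.822. The figure stands. It concerns toxicities, which are related events, and related anemia is collected.

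**5. Size.** If A is the true proportion of patients with non-serious anemia and s is the share judged at least possibly related, the recorded proportion is A × s. The documents give neither. As an illustration only, take A = 25%, the generic incidence in 16.21 and not an anemia estimate, with an assumed range for s:

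| s (assumed) | Recorded proportion, 0.25 × s |
|---|---|
| 1.00 | 25% |
| 0.75 | 18.75% |
| 0.50 | 12.5% |
| 0.25 | 6.25% |

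This shows the direction of the effect. It does not estimate it.

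**6. Scope.** Section 16.12 gives 49 to 58 patients including 40 in Phase Ib, so escalation contributes 49 − 40 = 9 to 58 − 40 = 18.

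**The case against.** The case on the other side is substantial, and much of it stands.

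- **The affected group is narrow.** Under 10.3, a possible attribution needs only that the event may be related. Anemia is listed above 10% for rucaparib (15.17) and among reactions at 30% or more for single-agent irinotecan (15.27). Few investigators may call it unlikely, so s could be close to 1. This stands, and is why no size is claimed.
- **Section 10.52 says in general terms that adverse events should be reported throughout, with no attribution limit.** True, but 10.531 is the specific rule for what goes on the Phase I/Ib forms. If some sites follow one and some the other, the rate becomes less consistent still.
- **A solicited list is a selection.** Several symptoms above 10% for rucaparib are also unsolicited, such as decreased appetite and constipation, as is lymphopenia (15.27). Anemia is singled out because routine blood counts allow it to be graded objectively at no extra burden.
- **Hemoglobin may already be on file.** Blood counts are scheduled at baseline and on days 1 and 15 (4.0), and 18.1 lists laboratory forms for those times. Leukopenia is also unsolicited yet has a planned nadir analysis, which suggests nadirs come from those forms. Their fields are not shown, so a reader who infers that hemoglobin is not collected goes beyond the documents.
- **The protocol treats anemia differently throughout.** It prompts no dose change (8.2), is exempt from discretionary reduction (8.3) and is not in the hematology rows of the DLT table (7.421). This is a clinical choice and does not make the tabulated rate unfiltered.

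A reader might also infer that treatment-related anemia is missed, or that the recommended dose is in doubt. Neither follows. Related anemia of any grade is collected, a DLT event must be assessed as at least possibly related (7.42), and the Phase I/Ib stopping rule (16.521) counts only related grade 4+ events.

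**Conclusion.** The point holds in a limited form and is minor. Followed as written, the Phase I/Ib collection rule gives an anemia rate in 16.231 that depends on attribution, next to neutrophil and platelet rates that do not. Any bias in the rate of all anemia is towards understatement. Its size is unknown.

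The conclusion rests on reading 10.531 as the operative rule for the AE forms and on the laboratory form fields being unseen, so it is shown for the AE forms and the analysis text only. MTD, recommended dose, stopping rules, sample size and the efficacy analyses are untouched.

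It should not be extended to Phase II in the same strength. There, grade 3-4 events are collected regardless of attribution, leaving only non-serious grade 1-2 anemia judged unrelated or unlikely. The plan makes no anemia comparison between phases, and their prior-therapy criteria differ.

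**What to change.** 1. Add an anemia row to 10.521, marked at baseline and at each evaluation.
2. Add anemia (hemoglobin) to the nadir and CTC-grade list in 16.232.
3. Under 16.231, not 16.232, specify a laboratory-derived summary of hemoglobin by CTCAE grade and by shift from baseline grade, regardless of attribution. It does not fit 16.232, which is confined to related events. State in 16.31 that the same summary applies to Phase Ib.
4. Note beside that summary that transfusion alters nadir and shift, and that 9.3 records blood products only in the medical records.

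Item 3 matters most. Section 7.12 shows that the recommended dose is already fixed, so a new solicited row reaches only visits still to come, whereas a laboratory summary can cover patients already treated. Lymphocytes could be added from the same differential at the sponsor's discretion.

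**Cost.** One more solicited term (15 to 16 at each evaluation, 14 to 15 at baseline), short text changes in 16.231, 16.232 and 16.31, and one more table. No new blood draw is needed. If the laboratory forms lack a hemoglobin field, one must be added and past values entered from source records.
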